3.2 Overview of the interventions

SHIELD intervention. The SHIELD intervention is based on social cognitive theory, which posits that positive behavior change requires knowledge and skills to increase behavioral capability, development of self-efficacy to increase the belief that one can achieve the desired outcomes, and social support to provide positive reinforcement and develop positive outcomes expectations.⁴⁶ We developed a modular program for AGYW that increases knowledge, skills, and self-efficacy to engage along the HIV prevention and care continuum, and a program for family members (up to four participants in addition to the AGYW; 10 years and older) to increase social support. To reflect AGYW's evolving cognitive and decisional capacity, judgement, emotional development, risk, and health-seeking behaviors, intervention content for both AGYW and families were tailored for five distinct groups to reflect development stage and

AGYW's HIV status. Content areas were adapted from existing evidence-based interventions, such as Stepping Stones^{30,31} and Families Matter!^{47,48} based on CAB and YAB input and formative research with AGYW, caregivers, and community leaders. Modules address HIV prevention and treatment, general wellness and SRH, approaches to combat stigma and discrimination, and skills for better communication, and include new content on health service availability and access to increase self-efficacy in seeking health care services. SHIELD educational materials were pre-tested. The SHIELD sessions will be offered to AGYW and their families in the 4 communities randomly assigned to intervention arms. The AGYW in the usual care arm will receive one education session focused on stigma and HIV care. SHIELD education session content is presented in **Exhibit 1** for the AGYW sessions and **Exhibit 2** for the family sessions. We have noted content that will be included in core sessions along with content that will be included in the basic education provided to the control group participants. The core sessions will be provided to all participants in the intervention communities while all other sessions will be optional content for future meetings within the intervention communities.

Exhibit 1. SHIELD Content Areas for Adolescent Girls and Young Women Program

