| HPV vaccination | Proportion receiving 1, 2, or 3 doses (IWC clinic only) | Clinic audit & visit data collection | HIV-/u & HIV+; 6m & 12m |
| Number of clinic visits | Proportion with visits at 6m and 12m; total number of visits | | |
| SRH services provided | Family planning, sexually transmitted diseases, and condoms | | |
| Baseline Data for AGYW | | | |
| Demographics & socio-economic status | AGEP baseline instrument | Self-report | All AGYW 24m |

Trained data abstractors will obtain the information from the clinical records at baseline and during the 6- and 12-month follow-up using prespecified abstraction forms. UNC's Zambia project manager will supervise the data collection at the IWC clinics that will manage the pre-screening processes, track visits, clinical services provided, and linkages for HIV care. Specially trained staff will perform biological data collection, which will include HIV testing at 12 months for the HIV-/u group, viral load testing at 12 months for the HIV+ group, and pregnancy testing for both groups at 12 months. All data collectors will be trained, data collection will undergo continual monitoring, and fidelity to protocol specifications will be confirmed by random in-person review of supervisors' data collection. IWC clinic staff will keep detailed records to track patient visits along with information on staff time spent across various clinic activities. Data will be stored locally at secure location at Population Council offices and reviewed for data completeness. Deidentified data then will be transferred securely to RTI and archived in secure,

password-protected servers. RTI staff will conduct further data quality review, produce reports, and develop analytic files.

SHIELD intervention exposure. Using attendance information entered in the study database, the study team will quantify the number of SHIELD education sessions AGYW and family members attend and the number of youth clubs AGYW attend. This will allow us to calculate the amount of exposure to the intervention (dose) for each participant. This dose estimate will be used as a covariate in sub analyses that examine the dose-response of the interventions on outcomes.

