Analysis of hypotheses. The **testing of the primary hypotheses** will be done by intent to treat, and the study team will examine the effects across the three randomization groups. Given the need to consider the influence of the cluster randomization by zone, The study team will use generalized estimating equation (GEE) models to estimate the effects of the randomization groups and will assess the need to apply small sample correction using approaches suggested by the NIH Health Care Systems Collaboratory Biostatistics and Design Core.⁵⁹ If the Hausman assumption of correlation between the random and fixed effects is violated, then The study team will include fixed effects representing cluster identification. The study team will adjust for baseline covariates, including sociodemographic factors and behavioral risks, should the initial descriptive analyses suggest differences in the distribution of these factors across study randomization groups. The study team will also explore the use of propensity scores to control for systematic differences between the groups. In further analyses, the study team will examine the potential mediating and moderating roles of key behavioral, social, and structural factors hypothesized to influence HIV testing and adherence along the HIV care continuum (e.g., social support; self-efficacy).. The study team will test the “dose” of the SHIELD training received as a covariate in these models. **Secondary analysis** will follow the same approach. As appropriate, the study team will perform analyses separately or pooled together for the HIV+ and HIV-/u cohorts. A key aspect of interest in this study is the developmental stage of the AGYW; using age as a proxy in our multivariate analysis, the study team will determine the differential effect of the IWC clinic and SHIELD intervention on outcomes reported by HIV status (see Exhibit 1 for groupings). In subsequent analyses, the study team will also consider both medium-term outcomes within the first 6 months after study enrollment and changes at any point during the 12-month follow-up period to assess longer-term outcomes. Additionally, for measures where we have baseline, 6-month and 12-month follow-up data (for example, self-efficacy, and other mediating outcomes for AGYW), the study team will perform difference-in-difference analysis, which will allow for comparisons between and across the study arms. The study team will also report all mediating factors, and 'IWC clinic utilization metrics stratified by age and HIV status to facilitate subgroup analysis. Importantly, the changes along the HIV care cascade, from HIV testing, linkage to care, ART adherence, and viral load suppression, will be documented to identify potential differential impacts of the interventions. This analysis is critical to assist in further tailoring the SHIELD training and IWC clinic services.

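### SHIELD dose, a post-randomisation and partly self-selected attendance count, is a planned covariate in the dose-response and mediation models and could reach secondary-endpoint models

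*Combined protocol and SAP*

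**What the plan says.** Section 3.3, under Analysis of hypotheses, says that testing of the primary hypotheses "will be done by intent to treat, and the study team will examine the effects across the three randomization groups", using "generalized estimating equation (GEE) models to estimate the effects of the randomization groups". It continues: "In further analyses, the study team will examine the potential mediating and moderating roles of key behavioral, social, and structural factors". The sentence after that brings in the dose "of the SHIELD training received as a covariate in these models", and the next one says that secondary analysis takes the same approach.

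Section 3.3, under SHIELD intervention exposure, defines dose from attendance records. The team will "quantify the number of SHIELD education sessions AGYW and family members attend and the number of youth clubs AGYW attend". It then says: "This dose estimate will be used as a covariate in sub analyses that examine the dose-response of the interventions on outcomes".

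Section 3.2 bears on how dose arises. Core sessions go to all participants in intervention communities, while "all other sessions will be optional content for future meetings within the intervention communities". For controls: "The AGYW in the usual care arm will receive one education session focused on stigma and HIV care".

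The plan gives no method for self-selected attendance. It does not say whether the control session counts as dose, whether the arm term stays in a dose model, or how that term would be read.

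**The concern.** Attendance is not a baseline covariate. It happens after randomisation, depends partly on who chooses to come, and is nearly determined by arm, since controls are offered one session and SHIELD participants many. Two problems follow.

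- **The dose slope.** It compares girls who attend more with girls who attend less. If motivation drives both attendance and HIV testing, the slope is confounded. The plan's rule for adding baseline covariates does not address this: it is triggered by differences between randomisation groups, not by what predicts attendance within the SHIELD zones.
- **The arm coefficient.** With dose in the model, it becomes the contrast extrapolated to zero sessions. That is not the intent-to-treat effect. It can be removed, because part of the effect has been conditioned away, or reversed, because a confounded slope is subtracted from it.

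At stake are the dose-response finding, which is itself a planned result, and any secondary-endpoint model that takes in dose through the same-approach sentence. Hypothesis 4 is the most exposed, because its contrast is SHIELD against no SHIELD for self-efficacy, social support and risk behaviour.

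**Working it through.** **1. The plan's own figure.** The documents give no figure on dose. The inputs borrowed below (200 per arm, 40% tested, two-sided 0.05, power 0.80) do reproduce the stated detectable difference of 13 to 14 points. With n = 200, p1 = 0.40, p2 = 0.5394 and mean 0.4697:

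1.96 × √(2 × 0.4697 × 0.5303 / 200) + 0.84 × √((0.24 + 0.2484) / 200) = 0.098 + 0.042 = 0.139, or 13.9 points.

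At n = 180, after 10% loss, the result is 14.7 points against the stated 15. No clustering allowance is included; that is a separate matter.

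**2. Which models contain dose.** The primary test is intent to treat by randomisation group. The exposure paragraph confines dose to sub analyses. In the analysis paragraph, the nearest antecedent of *these models* is the sentence on mediation and moderation. The same-approach sentence comes straight after the dose sentence and does not say whether dose is part of the approach.

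**3. Size with no true effect.** Inputs from section 3.3: 200 controls, 400 SHIELD girls (two arms of 200), 40% base rate. Assumptions, because attendance is not reported: correlation of motivation with testing 0.16; mean dose divided by its SD in SHIELD zones 2.13; control dose zero; no clustering; linear probability model. Let ρ be the correlation of motivation with attendance.

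- SD of the outcome: √(0.4 × 0.6) = 0.490.
- Dose-testing correlation: 0.16ρ.
- Arm shift: −(0.16ρ) × 0.490 × 2.13 = −0.167ρ.
- False dose-response: the slope is estimated in 400 girls, so its z is about 0.16ρ × √400 = 3.2ρ. The chance of p < 0.05 is about Φ(3.2ρ − 1.96) + Φ(−3.2ρ − 1.96).

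| ρ | Arm shift, formula (points) | Arm shift, simulated (points) | Dose significant, formula | Dose significant, simulated |
|---|---|---|---|---|
| 0.1 | −1.7 | about −2 | 6% | about 7% |
| 0.3 | −5.0 | about −5 | 16% | 15–17% |
| 0.5 | −8.4 | about −8 | 36% | 35–39% |
| 0.86 | −14.4 | −14 to −15 | 79% | 78–84% |

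Without dose in the model, the simulated arm effect stays at zero.

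**4. A true 15-point effect acting wholly through dose, no confounding.** The slope per session is 0.15 / mean dose. The arm coefficient is then 0.15 − (0.15 / mean dose) × mean dose = 0 when control dose is zero.

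**5. A second set of assumptions.** Three arms of 200; up to 12 sessions in SHIELD arms and one in control; about 59% attendance; a trait shifting testing by 10 points per SD (correlation about 0.10 / 0.490 = 0.20).

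- No true effect, confounded attendance: arm −19 to −20 points; dose falsely significant in 79–95%.
- True 15 points through dose, no confounding: arm 2 points, significant in 5%.
- True 15 points through dose, confounded: arm about −18 points.
- True 15 points not through dose, no confounding: arm unbiased at 14.9 points, but significant in 30% against 85% without dose.
- No true effect, no confounding: arm −0.5 points, dose significant in 5%, so no material bias.

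Across these runs the arm effect without dose stayed close to the truth: about 15 points with 84–87% power when the effect was real, and 4.6–5.4% rejection when it was not.

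**The case against.** The strongest defence is that the plan already keeps dose in its place. The primary hypotheses are tested by intent to treat, dose belongs to sub analyses, and no sentence says that an arm effect will be read from a dose model or that the arm term stays in it. A dose-response fit within SHIELD zones would be compatible with the exposure paragraph. This stands as far as the primary test goes. It does not rescue the dose slope, for which no method is given, and it does not settle what secondary analyses inherit.

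Three stronger readings are tempting, and the documents do not support them.

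- A reader might infer that the primary comparison is compromised. The intent-to-treat statement and the limit to sub analyses say otherwise.
- A reader might infer that dose adjustment must remove or reverse the arm effect. It does so only if the effect runs through attendance or attendance is confounded. With neither, the arm estimate is unbiased and only precision is lost. The larger shifts in step 3 need a motivation-attendance correlation near 0.86, which is close to extreme; at 0.1 the shift is about 2 points.
- A reader might infer that the dose result is what will guide tailoring of SHIELD. The tailoring sentence follows the one on changes along the HIV care cascade, so that link is not established.

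**Conclusion.** The concern holds in limited form. As written, the plan uses a post-randomisation, partly self-selected count as an ordinary covariate in the dose-response and mediation models, and leaves open whether secondary-endpoint models do the same. In any such model the dose slope can be confounded, and the arm coefficient does not estimate the intent-to-treat effect. This is a flaw in a stated method, not just missing detail. It does not reach the primary test.

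The direction is secure; the size is not. It rests on assumed attendance, an assumed motivation-testing correlation of 0.16 and no clustering, so the tabulated range should be read as a whole. The loss of an effect that acts wholly through dose needs no confounding at all.

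**What to change.** Add to Analysis of hypotheses, and mirror under SHIELD intervention exposure: *No model used to estimate or test an arm effect on a primary or secondary endpoint will include SHIELD dose. Dose-response is exploratory, is fitted within the SHIELD zones with prespecified baseline predictors of attendance, and is reported as an association.* List those predictors, and say that the same-approach sentence for secondary analysis does not carry dose with it.

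If an effect of attendance is wanted, an instrumental-variable (complier-average) estimate with assigned arm as instrument should be limited to SHIELD-only against control. In the third arm the IWC clinic can act on outcomes by routes other than sessions attended, which violates the exclusion restriction. With two zones per arm that comparison rests on four zones and will be imprecise.

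The cost is a few lines of text, a little extra analysis and a slightly weaker dose-response claim. Sample size and data collection do not change.

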1.2 Study Goal and Objectives

Our overall goal of the study is to test a multilevel package of interventions to connect AGYW with a source of regular care to provide a sustainable platform for successful implementation of regular HIV testing and support for linkage to care and adherence to antiviral treatment.

The objectives of the study are to:

1. Objective 1: Assess efficacy at 6, and 12 months of a multilevel integration intervention on HIV testing and viral load suppression.
2. Objective 2: Obtain feedback on the integrated care delivery model to assess sustainability, document best practices, and update SOPs to support scaling up of integrated services for AGYW.
3. Objective 3: Perform cost-effectiveness and budget analysis to evaluate and describe impact along the HIV care continuum and disseminate findings to national partners and the international community.

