Assess efficacy of the multilevel interventions (hypothesis testing). Cluster randomization study design and interventions. We propose a cluster randomized study implemented in the six selected geographic zones in Lusaka, each served by a government-operated clinic providing HIV and cervical cancer screening services. Zones, with their respective clinics, will be randomized into three groups (zones with IWC clinics and SHIELD intervention, zones with only SHIELD intervention, and control zones with no IWC clinic or SHIELD interventions. AGYW in the control zones will be offered one education session on HIV prevention and treatment) to assess the impact of offering IWC clinics coupled with the SHIELD intervention compared to the standard of care (see Exhibit 1 above). The study team will also evaluate whether a similar impact can be achieved with control clinics when the SHIELD intervention is offered in the community. The SHIELD intervention, as described in Section 3.2, will begin with training sessions for AGYW and their families. This will be followed by PN-facilitated youth clubs that will meet about once a month during the 12-month study timeframe. Two-four PNs will be assigned to each clinic zone with the SHIELD intervention, and one-two PN each will be assigned to the two control clinic zones to assist with data collection and follow-up activities. The PNs in zones with the IWC clinics will also serve as community liaisons to support clinic-community linkages. The health centers in which the **primary endpoint for the HIV/u cohort** is the proportion with any HIV testing at 12 months. **For the HIV+ cohort, we plan to assess the primary endpoint:** viral load suppression, measured as proportion with undetectable viral load at 12 months. The secondary endpoints are the proportion with decrease in HIV risk behavior, repeat HIV testing (each 6-month period), HIV infections diagnosed through voluntary HCT, linkages to HIV care, and adherence to ART. We will also conduct a targeted 6-month post-intervention data collection after the end of the 12-month intervention period. See **Exhibit 4** for endpoint definitions and biological, self-report, and clinic audit measures collected at 6- and 12-month follow up. To assess the impact of the SHIELD intervention on the mediating outcomes, the study team will collect data from AGYWs across all six clinic zones at baseline and at 6- and 12- month follow-up. The study team will also track health care service use by conducting clinic audits at all six clinic sites. We plan to retain the intervention cohort for a maximum of 24 months total to allow for initiation of the intervention and follow-up activities (12 months of intervention and follow-up after intervention completion).

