
Exhibit 4. Tables of measures at baseline, 6 months (6m), and 12 months (12m); few measures also collected at about 24 months (24m) during the post intervention period.

| Constructs/Measures | Instrument and Specification | Source | Cohort |
|---|--|-----------------------------|---|
| Primary and Secondary Endpoints—HIV Care Continuum and HIV Risk Behavior | | | |
| HIV testing; proportion tested for HIV in the past 6 and 12 months | Abstraction tool (serologic HCT); and self-report confirmed via clinic audit; repeat HCT at 6-month intervals will be assessed | Clinic audit Self-report | HIV-/u 6m,12m Self report only at 24m |
| HIV early detection; proportion with HIV identified through voluntary testing | All participants will be tested to determine HIV status (rapid finger prick and follow-up per Zambian guidelines) | Biological | HIV-/u 12m |
| Linkage to care: proportion enrolled at an HIV clinic in ≤ 30 days; ART initiated in ≤ 90 days | Measured as days from testing HIV positive or from baseline when not on treatment (HIV+ but not on ART) | Clinic audit | HIV-/u HIV+ 6m & 12m |

| | | | |
|--|--|--------------------------------------|--|
| Adherence to ART; proportion filling prescriptions at least every 3 months | Zambian guidelines recommend dispensing 3-month supply of ART medications | Clinic audit Self-report | HIV+ 6m &12m Self-report only at 24m |
| Viral load suppression; proportion with undetectable viral load | HIV plasma viral load tests using the Roche platform | Biological | HIV+ 6m &12m |
| HIV risk behavior: proportion with delay in first intercourse, reduction in sexual partners; increases in condom use | Demographic and Health Survey and AGEP instrument (measures will be based on previous studies by grant team, including AGEP) | Self-report | HIV-/u Baseline, 6m, 12m & 24m |
| AGYW (Mediating outcomes, SHIELD intervention dose, and clinic-based services) | | | |
| Self-efficacy, social support, HIV stigma & gender roles | Tailored instrument based on supplemental survey completed at cohort recruitment | Self-report | HIV-/u & HIV+ Baseline, 6m, & 12m |
| Mental health and substance abuse | Brief assessment based on NICHD consortium common data elements | Self-report | |
| Unintended pregnancy | Tested at 12m | Urine test | |
| Education modules (AGYW & family) | Number of modules completed | Study database | Self-report at 24m |
| Youth club attendance | Number and proportion of meetings attended | | |

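### Longer-term outcomes are assessed by changes at any point in 12 months, so in the subsequent analyses an effect seen only in the first 6 months could be labelled longer-term

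*Combined protocol and SAP*

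**What the plan says.** Objective 1 (Section 1.2) names two time points: "Assess efficacy at 6, and 12 months of a multilevel integration intervention on HIV testing and viral load suppression". Section 3.3 fixes the primary endpoints at 12 months. For the HIV-/u cohort the endpoint "is the proportion with any HIV testing at 12 months"; for the HIV+ cohort it is viral suppression, "measured as proportion with undetectable viral load at 12 months".

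After the primary and secondary analyses, the Analysis of hypotheses text sets two horizons: "In subsequent analyses, the study team will also consider both medium-term outcomes". The medium-term horizon is "medium-term outcomes within the first 6 months after study enrollment". The longer-term horizon is "changes at any point during the 12-month follow-up period to assess longer-term outcomes". No other section defines longer-term outcomes.

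Exhibit 4 schedules ART adherence and viral load at 6 and 12 months, and the mediating scales at baseline, 6 and 12 months. Risk behaviour has those three time points and 24 months as well. For HIV testing, "repeat HCT at 6-month intervals will be assessed".

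**The concern.** The two horizons are meant to separate early effects from later ones, but the second contains the first. An any-point outcome tests whether there was an effect in either half of the year. A longer-term question asks whether there is an effect late in the year. When the effect is confined to months 1-6, the any-point null is false and the late null is true.

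This matters for outcomes that can go back to where they started. A participant who is adherent, or reports higher self-efficacy, at 6 months and has reverted by 12 months still counts as having changed at some point. Conversely, participants already counted at 6 months leave less room for an effect that appears only at 12 months. At stake is whether a statement about durability in these analyses means what it says. It matters less for cumulative outcomes such as any HIV test in 12 months, where an any-point definition is natural, although an early test would still be labelled longer-term.

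**Working it through.** The plan states no figure for this analysis, so there is none to reproduce. The point follows from the wording, and the arithmetic only shows its possible size.

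**The windows.** Medium-term covers months 0-6. Longer-term covers any point in months 0-12. The first lies wholly inside the second, and nothing requires a change to be present at month 12.

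**Inputs.** The control suppression rate of 70% is the lower end of the plan's 70 to 75%, and the 15-point effect is the plan's target improvement (both from the sample-size text in Section 3.3). The remaining inputs are assumptions: the effect is present at 6 months and wholly gone at 12, and the within-person correlation φ between the two visits runs from 0 to 0.7. The illustration treats the outcome as positive at either visit, which is one reading of a change at any point.

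**Formula.** With p6 and p12 the proportions positive at the two visits:

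- P(both) = p6·p12 + φ·√[p6(1−p6)·p12(1−p12)], which cannot exceed the smaller of p6 and p12
- P(any point) = p6 + p12 − P(both)

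**Worked case, φ = 0.5.**

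- Control (70%, 70%): P(both) = 0.49 + 0.5 × 0.21 = 0.595, so P(any) = 1.40 − 0.595 = 0.805.
- Intervention (85%, 70%): P(both) = 0.595 + 0.5 × √(0.1275 × 0.21) = 0.595 + 0.5 × 0.1636 = 0.677, so P(any) = 1.55 − 0.677 = 0.873.
- Difference: 6.8 points. Difference at 12 months: 70% − 70% = 0.

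| φ | Control, any point | Intervention, any point | Difference |
|---|---|---|---|
| 0 | 91.0% | 95.5% | 4.5 points |
| 0.3 | 84.7% | 90.6% | 5.9 points |
| 0.5 | 80.5% | 87.3% | 6.8 points |
| 0.7 | 76.3% | 85.0% | 8.7 points |

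**Limit on the last row.** For 85% and 70% the largest possible correlation is (0.70 − 0.595)/0.1636 = 0.64. At 0.7 the intervention arm is therefore held at its ceiling, P(both) = 0.70. With a common correlation of 0.64 in both arms, control is 1.40 − (0.49 + 0.6417 × 0.21) = 0.775 and intervention is 0.850, a difference of 7.5 points. The same ceiling is 0.577 for 90% and 75%, so at the 75% base rate a correlation of 0.6 cannot occur.

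**Rarer outcome.** A reverting outcome of 55% v 40% at 6 months and 40% v 40% at 12 gives 73.0% v 64.0% (9.0 points) at φ = 0 and 55.9% v 47.2% (8.7 points) at φ = 0.7.

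**Effect at 12 months only.** The formula is symmetric in p6 and p12. A 15-point effect confined to month 12 therefore appears as the same 4.5 to 8.7 points under the any-point outcome at the 70% base rate. That is the dilution.

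**Viral load timing.** The viral load example needs a 6-month test. Exhibit 4 lists one in the row "Viral load suppression; proportion with undetectable viral load", but the data-collection text after the exhibit describes viral load testing at 12 months only. Exhibit 4 lists no baseline viral load, so a change in suppression is not fully defined either.

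**The case against.** The strongest reply is that this is one exploratory sentence in a plan that already looks at the later period. Viral suppression at 12 months is a primary endpoint. Repeat HIV testing within each 6-month period is a secondary endpoint, so months 7-12 are covered, and the secondary analysis follows the primary approach. Difference-in-difference is planned for measures with baseline, 6- and 12-month data. All of this stands and limits the point. A reader might infer that the plan's longer-term conclusion rests on the any-point analysis; the documents do not support that. What they lack is a rule for which result may be called longer-term: the difference-in-difference text names no contrast as such.

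A reader might also infer a large false-positive rate from HIV testing. A 15-point cumulative gain (40% v 55%, 180 per arm, clustering ignored) produced entirely in months 1-6 would be detected about 82% of the time. That is the ordinary power of the cumulative 12-month comparison, which is in substance the primary endpoint. It is correct detection of a real difference, and only the label longer-term would be wrong.

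It is also fair that the sentence specifies no model and speaks of changes, so positive at either visit is an interpretation. Nor do the documents establish that effects will fade: SHIELD starts with training sessions, but youth clubs continue about monthly through the 12 months.

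**Conclusion.** The point holds as a definitional fault in the subsequent analyses. As written, an effect present only early could be labelled longer-term for ART adherence, self-efficacy, social support and risk behaviour, and for viral suppression if the 6-month test is done. An effect present only at 12 months would be diluted.

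In the suppression illustration the any-point difference is 4.5 to 8.7 points when the 12-month difference is zero, or 4.5 to 7.5 points if one feasible correlation applies to both arms. These sizes depend on assumed correlations, a fully vanishing effect and the positive-at-either-visit reading. The overlap of the windows depends on none of them. The primary tests are not affected.

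**What to change.** In Section 3.3, Analysis of hypotheses:

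- Define longer-term outcomes as status, or change from baseline where a baseline exists, at 12 months. For HIV testing, use months 7-12 through the existing secondary endpoint of repeat testing by 6-month period.
- Where both time points exist, estimate the 6- and 12-month arm effects with arm-by-time terms in the planned GEE, and base any longer-term statement on the 12-month (or months 7-12) estimate.
- Keep any-point results if wanted, but call them cumulative.
- Reconcile Exhibit 4 (viral load at 6 and 12 months) with the data-collection text after it (12 months only), and state what a change in suppression means without a listed baseline value.

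The cost is analysis-plan wording. The later-period measures are already scheduled, so no new visits, participants or data are needed.
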